## 7.0 Adverse events

### 7.1.1 Contraindications:

Known allergy to ceritinib, no specific contraindications listed in package insert.

### 7.1.2 Special Warnings and Precautions for Use:

Cardiac: symptomatic bradycardia can occur with heart rate <50/min. If possible, will avoid concurrent use of agents that may cause bradycardia (eg, beta blockers, nondihydropyridine calcium channel blockers, clonidine, digoxin). Will monitor heart rate and blood pressure regularly. Dose will be held for symptomatic bradycardia.

QTc prolongation: QTc interval prolongation has occurred in clinical studies, and may be concentration-dependent. Will periodically monitor ECG and electrolytes in patients with heart failure, bradyarrhythmias, electrolyte abnormalities, or who are taking medications known to prolong the QTc interval. May require treatment interruption, dosage reduction, or discontinuation. Will permanently discontinue in patients who develop QTc interval prolongation in combination with torsades de pointes or polymorphic ventricular tachycardia or signs/symptoms of serious arrhythmia.

Gastrointestinal toxicity: Diarrhea, nausea, vomiting, or abdominal pain occurred in the majority of patients in clinical trials; over one-third of patients required dose reductions due to severe or persistent gastrointestinal toxicity. Symptomatic management will be with antiemetics and antidiarrheals.

Hepatotoxicity: Hepatotoxicity has been observed in patients treated with ceritinib in clinical trials, including ALT levels >5 times ULN in over one-quarter of patients.

Hyperglycemia: Hyperglycemia, including grade 3 and 4 toxicity, has been observed in ceritinib-treated patients. Close monitoring of blood sugars in patients with baseline random blood sugar greater than 180, with addition of insulin or other medication to correct hyperglycemia.

Pulmonary toxicity: Severe and life-threatening interstitial lung disease (ILD)/pneumonitis (some fatal) may occur. Monitor for signs/symptoms of pulmonary toxicity; permanently discontinue in patients diagnosed with treatment related ILD/pneumonitis.

### 7.1.3 Interaction with other medications

CYP3A inducers and inhibitors: these should be avoided while patients are receiving ceritinib. If a strong CYP3A inhibitor must be given concurrently, the dose of ceritinib should be reduced. Similarly concurrent administration of substrates of CYP3A and CYP2C9 should also be avoided.

Please note Section 14.1 for a full list of medications that require caution.

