  8. Impaired GI function or GI disease that may alter absorption of ceritinib or inability to swallow up to five ceritinib capsules daily. Although, patients unable to swallow capsules will be allowed to participate in this study, by following the specific instructions on making a slurry of the medication.
  9. Patient has impairment of GI function or GI disease that may significantly alter the absorption of ceritinib (e.g., ulcerative diseases, uncontrolled nausea, vomiting, diarrhea, or malabsorption syndrome).
  10. Receiving medications that meet one of the following criteria and that cannot be discontinued at least 1 week prior to the start of treatment with ceritinib and for the duration of participation (see Appendix 1 Tables):
    - Medication with a known high risk of prolonging the QT interval or inducing Torsades de Pointes (please refer to <http://www.azcert.org/medical-pros/drug-lists/drug-lists.cfm>)
    - Strong inhibitors or strong inducers of CYP3A4/5 (please refer to <http://medicine.iupui.edu/flockhart/table.htm> or <http://www.druginteractioninfo.org>)
    - Medications with a low therapeutic index that are primarily metabolized by CYP3A4/5, CYP2C8 and/or CYP2C9 (please refer to <http://medicine.iupui.edu/flockhart/table.htm> or <http://www.druginteractioninfo.org>)
    - Therapeutic doses of warfarin sodium (Coumadin) or any other coumadin-derived anti-coagulant. Anticoagulants not derived from warfarin are allowed (eg, dabigatran, rivaroxaban, apixaban).
    - Unstable or increasing doses of corticosteroids; If patients are on corticosteroids for endocrine deficiencies or tumor-associated symptoms (non-CNS), dose must have been stabilized (or decreasing) for at least 5 days before first dose of study treatment.
    - Enzyme-inducing anticonvulsive agents
    - Herbal supplements
  11. Pregnant or nursing (lactating) women, where pregnancy is defined as the state of a female after conception and until the termination of gestation, confirmed by a positive hCG laboratory test.
  12. Women of child-bearing potential, defined as all women physiologically capable of becoming pregnant, unless they are using highly effective methods of contraception during dosing and agree to continue for 3 months after the last dose of study treatment. Highly effective contraception methods include:

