#### **4.4 Concomitant medications**

In general, the use of any concomitant medication/therapy deemed necessary for the care of the patient (e.g., anti-emetics, anti-diarrheal agents) is permitted, except when specifically prohibited. The patient must be told to notify the investigational site about any new medications he/she takes after the start of the ceritinib treatment. All medications, including herbal/natural medications (excluding ceritinib treatment and prior antineoplastic treatments and blood transfusions), surgeries and procedures (including physical therapy) administered within 30 days prior to the first dose of administration of ceritinib treatment through 30 days after the last dose of ceritinib treatment will be recorded. Medications include not only physician prescribed medications, but also all over-the counter (OTC) medications, herbal medications (prohibited, see [Section 4.4.2](#)), food or vitamin supplements, and blood transfusions.

For up to date information on prohibited medications please refer to the following websites:

- Medication with a known High risk of prolonging the QT interval or inducing Torsades de Pointes (please refer to <http://www.azcert.org/medical-pros/drug-lists/drug-lists.cfm> )
- Strong inhibitors or strong inducers of CYP3A4/5 (please refer to <http://medicine.iupui.edu/flockhart/table.htm> or <http://www.druginteractioninfo.org> )

- Medications with a low therapeutic index that are primarily metabolized by CYP3A4/5, CYP2C8 and/or CYP2C9 (please refer to <http://medicine.iupui.edu/flockhart/table.htm> or <http://www.druginteractioninfo.org>)

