##### 4.4.1.2 Drugs that are metabolized by CYP450 enzymes

*In vitro* drug metabolism studies show that the metabolism of ceritinib is mediated by CYP3A4/5. Ceritinib is a time-dependent CYP3A4/5 inhibitor and is also a potent reversible inhibitor of CYP2A6, 2B6, 2C8, 2C9 and 3A4/5 and may consequently increase exposure to drugs metabolized by these enzymes. Clinical studies have not yet been performed to confirm the potential effect of ceritinib on substrate drugs metabolized by these enzymes in patients. Also, the potential effect of low and moderate CYP3A4/5 inhibitors and inducers on ceritinib clearance is not known.

Concomitant treatment of ceritinib with weak inhibitors or inducers of CYP3A4/5 is permitted. Caution is advised when ceritinib is co-administered with drugs that are moderate inhibitors or inducers of CYP3A4/5 (Appendix 1). Duration of concomitant treatment should be kept as short as possible, or completely avoided whenever possible. Patients receiving such medications must be monitored closely for any potentiation of toxicity or decrease of clinical benefit due to any individual concomitant medications, and may require dose titration or adjustment. Note that co-administration of ceritinib with strong inducers or inhibitors of CYP3A4/5 is prohibited (Section 4.4.2.5).

Concomitant treatment of ceritinib with medications known to be metabolized by CYP2A6, 2B6, 2C8 and 2C9 is allowed with caution (Appendix 1), except for drugs which have narrow therapeutic index/sensitive substrates for these CYP isoforms (Section 4.4.2.6 and Appendix 1).

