#### 4.4.2.5 Strong CYP3A inhibitors and inducers

*In vitro* metabolism studies suggest that oxidative metabolism of ceritinib is predominantly mediated by CYP3A4/5.

Strong inhibitors or inducers of CYP3A4/5 are prohibited. Patients receiving concomitant medications known to strongly inhibit and/or induce CYP3A4/5 that are deemed medically necessary should be excluded from the study. Refer to [Appendix 1](#) for a list of these medications. Please note that this list may not be comprehensive.

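### Section 7.1.3 provides for a strong CYP3A inhibitor alongside a reduced ceritinib dose, while exclusion criterion 10, Section 4.4 and Table 14-1 prohibit the combination

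*Combined protocol and SAP*

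**What the plan says.** Exclusion criterion 10 (Section 3.3) is introduced with "Receiving medications that meet one of the following criteria and that cannot be discontinued at least 1 week prior to the start of treatment" and extends to the whole of participation; strong CYP3A4/5 inhibitors are one of its listed classes. Section 4.4 repeats the class under "For up to date information on prohibited medications please refer to the following websites".

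Section 4.4.1.2 permits weak CYP3A4/5 inhibitors, advises caution with moderate ones, and then states: "Note that co-administration of ceritinib with strong inducers or inhibitors of CYP3A4/5 is prohibited". Section 4.4.2.5 states: "Strong inhibitors or inducers of CYP3A4/5 are prohibited". It also deals with medical need: "Patients receiving concomitant medications known to strongly inhibit and/or induce CYP3A4/5 that are deemed medically necessary should be excluded from the study". Appendix 1, Table 14-1 names the strong inhibitors under a heading of prohibited medications.

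Section 7.1.3, in the adverse-events chapter, opens with "CYP3A inducers and inhibitors: these should be avoided while patients are receiving ceritinib". Its next sentence is "If a strong CYP3A inhibitor must be given concurrently, the dose of ceritinib should be reduced". It ends by sending the reader to Section 14.1 for drugs that require caution.

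**The concern.** Two instructions written for investigators address the same event, a strong inhibitor that the patient needs, and give different answers. Under one the combination is not allowed at all. Under the other the patient continues ceritinib at a lower dose that is not specified.

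The protocol itself treats this interaction as a safety matter. Section 1.3.1.1.2 names CYP3A4/5 as the major hepatic enzyme metabolising ceritinib in a human in vitro system. Section 7.1.2 says that QTc prolongation may depend on concentration. The QTc procedure in Table 4-3 asks the site to review concomitant drugs for their potential to inhibit CYP3A4/5. Section 11.5 requires the study to be run exactly as the approved protocol describes, so two investigators could act in opposite ways and each could cite the protocol.

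**Working it through.** The plan gives no figure on this point, so the check is a comparison of text.

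**1. What each place says about strong CYP3A4/5 inhibitors**

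| Place | Status | If the drug is needed |
|---|---|---|
| Section 3.3, exclusion 10 | Excluded if it cannot be stopped | Patient not eligible |
| Section 4.4 | Listed as prohibited, with website references | Not stated |
| Section 4.4.1.2 | Prohibited | Not stated |
| Section 4.4.2.5 | Prohibited | Exclude from the study |
| Table 14-1 | Prohibited | Not stated |
| Section 7.1.3 | To be avoided | Give it, with a reduced ceritinib dose |

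Five places bar the class, or four if the list in Section 4.4 is counted only as a pointer to websites. One place provides for use. No sentence makes Section 7.1.3 an exception, marks it as background, or ranks one section above another.

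**2. When the conflict arises.** Exclusion 10 removes patients who already depend on such a drug. What remains is mainly a need that begins after ceritinib has started. The exclusion sentence in Section 4.4.2.5 reads most naturally as a screening rule, and that section states no on-treatment consequence. Other sections do state one: Section 4.4.2.4 says what happens when a patient cannot avoid an enzyme-inducing anti-epileptic, and Section 4.4.2.1 does so for other anticancer therapy. For a strong inhibitor needed on treatment, Section 7.1.3 is the only text that says what to do, and it conflicts with the prohibition.

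**3. Whether Section 7.1.3 can be followed as written.** It gives no amount. Table 4-2 has three levels (450, 300 and 150 mg daily), bases reductions on the worst preceding toxicity, and allows nothing below 150 mg/day. A patient already at the lowest level has no reduction available under that table. Section 4.2 permits no dose escalation, and nothing says what happens to the dose once the inhibitor is stopped. The nearest related text is a remark in Section 4.4.1.2 that patients on moderate inhibitors or inducers may need dose adjustment; it also gives no amount.

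**4. The appendix tables.** Table 14-1 lists 3 macrolides + 6 antivirals + 4 antifungals + 4 others = 17 strong inhibitors. Four of them also appear in Table 14-2, the use-with-caution list: clarithromycin and telithromycin as CYP3A4/5 substrates, tipranavir as a moderate inducer, and ritonavir as both. A reader who follows Section 7.1.3 to the caution list finds drugs there that the preceding table prohibits. The cross-reference adds to the confusion: Section 7.1.3 cites Section 14.1, while the body numbers this appendix 13.1.

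**The case against.** The best defence is that Section 7.1.3 is descriptive safety text, close to references to the package insert, and that Sections 3.3 and 4.4 govern concomitant drugs. It tells the reader to avoid CYP3A inhibitors first, and the dose sentence applies only when one must be given. The appendix that it cites contains the table prohibiting strong inhibitors. Much of this stands: Section 7.1.3 is not a general permission, and the open case is narrow. It does not remove the conflict, because the sentence is worded as an instruction, covers the very need that Section 4.4.2.5 answers differently, and is not subordinated to any other section.

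Table 14-2 can also be defended, since it lists the four drugs for other properties (substrate or moderate inducer). That explains the overlap but does not tell a site whether the drug may be given.

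A reader might infer a stronger point: that the investigator must either stop ceritinib, which counts as a PFS event, or continue, which does not, so that the primary endpoint turns on which section is read. The documents do not support this. The PFS definition in Sections 2.0 and 9.1 counts discontinuation of the trial for any other reason, and stopping ceritinib for a drug interaction is not shown to be the same thing. Section 1.3.3 comes nearest: it ends participation when ceritinib is no longer the systemic agent, but it is describing later progression. Nor are stopping and continuing the only outcomes the protocol recognises. Section 4.3 accepts interruptions of up to one 28-day cycle, and longer ones by agreement, although it is written for toxicity.

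Expressing one patient as 1/18 = 5.6% of cohort A or 1/15 = 6.7% of cohort B does not rescue the inference. Those are shares of planned patients, not of PFS events, and they say nothing about how often a strong inhibitor would be needed.

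**Conclusion.** The inconsistency is real and can be confirmed from the text alone. Four places prohibit strong CYP3A4/5 inhibitors, a fifth lists them as prohibited, and one provides for their use with a dose reduction that the dose-modification rules do not define. Table 14-2 compounds this for 4 of the 17 named drugs.

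The consequence is for patient safety and uniform conduct, mainly when the need arises on treatment. Its frequency cannot be estimated from the documents. No effect on sample size, power or the primary PFS analysis is shown. The conclusion assumes only that Section 7.1.3 is in force as written, since nothing in the documents says otherwise.

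**What to change.** The sponsor's clinical team should reconcile exclusion criterion 10, Sections 4.4, 4.4.1.2, 4.4.2.5 and 7.1.3, and Tables 14-1 and 14-2, so that one rule applies to a strong CYP3A4/5 inhibitor that becomes necessary on study. The rule should be complete enough for a site to follow without choosing between sections, and consistent with Section 4.3 and Table 4-2. Three smaller corrections belong in the same edit:

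- Settle the status of clarithromycin, telithromycin, ritonavir and tipranavir across the two tables.
- Align the unqualified advice in Section 7.1.3 to avoid CYP3A inhibitors with Section 4.4.1.2, which permits weak ones.
- Correct the appendix cross-reference.

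This review takes no position on which rule or dose is right. The cost is protocol wording, with the IRB approval that Section 11.6 requires for an amendment. Sample size and the planned analyses are unaffected.

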### 7.1.4 Adverse Reactions

In the dose escalation phase patients were treated on a once daily schedule at the following dose levels: 50 mg, 100 mg, 200 mg, 300 mg, 400 mg, 500 mg, 600 mg, 700 mg and 750 mg. The MTD was determined to be 750 mg daily. Following determination of the MTD in May-2012 the expansion part of the study opened at the 750 mg daily dose level.

During the dose escalation part of the study, first cycle dose-limiting toxicities (DLTs) that contributed to the definition of the MTD included hypophosphatemia (400 mg), ALT elevation (400 mg), nausea with dehydration (600 mg), diarrhea (600 mg and 750 mg), and vomiting (750 mg). There were 3 cases of grade 3 hypophosphatemia, one of which was a DLT that contributed to the MTD determination – this patient was able to continue ceritinib at the same dose. In all cases patients were able to continue therapy without dose modification. Hypophosphatemia was not among the most commonly reported AEs (i.e., < 10%), regardless of relationship to ceritinib treatment.

The majority of adverse events, regardless of relationship to study drug, have been Grade 1-2, and have not required dose interruption or reduction. The most common adverse events were gastrointestinal toxicities, including nausea, diarrhea and vomiting, occurring in 72.7%, 72.7%, and 55.5% of patients, respectively. Other adverse events occurring in more than 20% of patients included fatigue (30.9%), abdominal pain (27.3%), decreased appetite (25.9%), ALT increased (25.0%) and constipation (21.4%). Grade 3 and 4 adverse events were much less common, with none occurring in 16% or more of patients. ALT increase, AST increase and diarrhea were the most common grade 3 or 4 events, occurring in

15.5%, 7.3% and 5.9% of patients, respectively. All other grade 3 or 4 events occurred in less than 5% of patients.

Preliminary ECG data from 220 patients treated at doses of 50-750 mg suggest that ceritinib may have an effect on the QT interval. One patient (700 mg QD dose; <1%) had a QTc > 500 msec and 2 (1.6%) patients (1 at 700 mg QD dose, 1 at 750 mg QD dose) had an increase from baseline QTc > 60 msec.

Interstitial lung disease/pneumonitis has been reported in some patients treated with ceritinib. Five cases improved or resolved with interruption of ceritinib and treatment with antibiotics and/or steroids. In one case, ceritinib was resumed at a reduced dose without recurrence of pneumonitis. Recurrent pneumonitis has also been reported following re-challenge of cases at a lower dose of ceritinib. Two fatal outcome of treatment-related pneumonitis has been reported.

In summary, ceritinib has been generally well tolerated by patients with *ALK*-rearranged NSCLC at doses up to the MTD of 750 mg daily. GI toxicities are common, but they are generally grade 1-2, and resolve with holding ceritinib and reducing the dose in the setting of grade 3-4 events.

## 7.2 Adverse Event Monitoring

Adverse event data collection and reporting, which are required as part of every clinical trial, are done to ensure the safety of subjects enrolled in the studies as well as those who will enroll in future studies using similar agents. Adverse events are reported in a routine manner at scheduled times during a trial. Additionally, certain adverse events must be reported in an expedited manner to allow for optimal monitoring of subject safety and care.

All subjects experiencing an adverse event, regardless of its relationship to study drug, will be monitored until:

- the adverse event resolves or the symptoms or signs that constitute the adverse event return to baseline;
- any abnormal laboratory values have returned to baseline;
- there is a satisfactory explanation other than the study drug for the changes observed; or
- death

### 7.2.1 Definition

An adverse event is defined as any untoward or unfavorable medical occurrence in a human research study participant, including any abnormal sign (for example, abnormal physical exam or laboratory finding), symptom, clinical event, or disease, temporarily associated with the subject's participation in the research, whether or not it is considered related to the subject's participation in the research. Adverse events encompass clinical, physical and psychological harms. Adverse events occur most commonly in the context of biomedical research, although on occasion, they can occur in the context of social and behavioral research. Adverse events may be expected or unexpected.

#### Severity

Adverse events will be graded by a numerical score according to the defined NCI Common Terminology Criteria for Adverse Events (NCI CTCAE) and version number specified in the protocol. Adverse events not specifically defined in the NCI CTCAE will be scored on the Adverse Event log according to the general guidelines provided by the NCI CTCAE and as outlined below.

- Grade 1: Mild
- Grade 2: Moderate
- Grade 3: Severe or medically significant but not immediately life threatening
- Grade 4: Life threatening consequences
- Grade 5: Death related to the adverse event

## Serious Adverse Events

ICH Guideline E2A and the UTSW IRB define serious adverse events as those events, occurring at any dose, which meets any of the following criteria:

- Results in death
- Immediately life-threatening
- Results in inpatient hospitalization or prolongation of existing hospitalization
- Results in persistent or significant disability/incapacity
- Results in a congenital anomaly/birth defect
- Based upon appropriate medical judgment, may jeopardize the subject's health and may require medical or surgical intervention to prevent one of the other outcomes listed in this definition.

Note: A "Serious adverse event" is by definition an event that meets **any** of the above criteria. Serious adverse events may or may not be related to the research project. A serious adverse event determination does not require the event to be related to the research. That is, both events completely unrelated to the condition under study and events that are expected in the context of the condition under study may be serious adverse events, independent of relatedness to the study itself. As examples, a car accident requiring overnight hospitalization would be a serious adverse event for any research participant; likewise, in a study investigating end-stage cancer care, any hospitalization or death would be a serious adverse event, even if the event observed is a primary clinical endpoint of the study. Refer to the UTSW IRB website at <http://www.utsouthwestern.net/intranet/research/research-administration/irb/study-management/adverse-events.html> to determine when a serious adverse event requires reporting to the IRB.

